9.5.8 Catheter Injection-site assessment

Injection-site assessment data will be listed and summarized in frequency tables by treatment, bolus administration mode and day.

9.5.9 Pain Measurements using the Visual Analog Scale (VAS)

Pain measurements during bolus application will be assessed using the electronic version of the 100-mm validated VAS (or electronic VAS [eVAS]) for pain. Data will be listed and summarized by treatment and bolus administration mode.

VAS data will also be summarized based on the following categories of score: 0 mm, 1-10 mm, 11-20 mm, 21-30 mm, 31-40 mm, etc. up to the maximum category by treatment and timepoint, and also the categories ≤ 10 mm, ≤ 20 mm and ≤ 45 mm. The table will show number and percent of patients with observations in each category.

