			Day -1	Day 1	Day 2	Day 3		
Plasma glucose monitoring with Super GL glucose analyzer (minutes)				-30, -15, 0, 10, 20, 30, 40, 50, 60, 70, 80, 90, 100, 110, 120, 135, 150, 165, 180, 195, 210, 225, 240, 300	-30, -15, 0, 10, 20, 30, 40, 50, 60, 70, 80, 90, 100, 110, 120, 135, 150, 165, 180, 195, 210, 225, 240, 300	-30, -15, 0, 10, 20, 30, 40, 50, 60, 70, 80, 90, 100, 110, 120, 135, 150, 165, 180, 195, 210, 225, 240, 300		Time is referenced to the start of the administration of the bolus dose of insulin lispro (LY900014 or Humalog) for the breakfast meal tests, that is, time 0.
VAS and insertion-site assessments (minute)				0 ^d , 20, 40, 60, 120, 180, 240, 300	0 ^d , 20, 40, 60, 120, 180, 240, 300	0 ^d , 20, 40, 60, 120, 180, 240, 300		Time is referenced to dose of insulin lispro (LY900014 or Humalog) for the breakfast test meals.
Assessment of insulin delivery experience						X		Subjects will be asked to provide the overall acceptability of their insulin delivery experience, either prior to CRU discharge or after completing Day 3 lunch procedures for each period.
Biomarker sample ^c (PGx)				Period 1 only (predose)				
Sample for immunogenicity ^c				Period 1 only (predose)			X	Additional samples may be collected if there is a possibility that an AE is immunologically mediated.

Abbreviations: AE = adverse event; CGM = continuous glucose monitoring; CRU = clinical research unit; ECG = electrocardiogram; ED = early discontinuation; FU = follow-up; MMTT = mixed-meal tolerance test; PK = pharmacokinetics; VAS = visual analog scale.

Note: Interim telephone visits may occur at any time during the outpatient periods, as determined by the investigator, to review the safety and well-being of the patient.

- a Patients should be fasted for at least 8 hours before the start of screening and follow-up (or early discontinuation) activities. Patients may consume up to 20 g of carbohydrates to treat or prevent hypoglycemia during the fasting periods.
- b Within 7 to 14 days after last dose or early discontinuation.
- c Predose is defined as the predose for the breakfast test meal only. Predose measurements should be performed within approximately 2 hours before the planned dosing time.
- d The VAS at the 0-minute time point is to be performed as soon as practicably possible after the start of the dosing for the breakfast meal tests.

3. Introduction

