To evaluate the difference in insulin lispro PK when LY900014 and Humalog are administered as different test bolus doses with an insulin pump to patients with T1DM during a breakfast meal test	AUC, C _{max} , T _{max} , early 50% T _{max} , and late 50% T _{max}
Secondary Objectives	Endpoints
To evaluate the sustainability of any difference in insulin lispro PK of LY900014 and Humalog over 3 days when administered as different test bolus doses with an insulin pump to patients with T1DM during a breakfast meal test	AUC, C _{max} , T _{max} , early 50% T _{max} , and late 50% T _{max}
To evaluate the difference in GD response when LY900014 and Humalog are administered as different test bolus doses with an insulin pump to patients with T1DM during a breakfast meal test	ΔAUC
To compare the durability of GD response over 3 days when LY900014 and Humalog are administered as different test bolus doses with an insulin pump to patients with T1DM during a breakfast meal test	ΔAUC
Exploratory Objectives	Endpoints
To evaluate the safety and tolerability of LY900014 administered with an insulin pump	Adverse events, anti-insulin lispro antibodies, infusion-site reactions/pain, and frequency and/or severity of hypoglycemia
To compare the GD response using CGM when LY900014 and Humalog are administered as different test bolus doses with an insulin pump to patients with T1DM during a standardized lunch meal	ΔAUC
To compare the GD response using CGM when LY900014 and Humalog are administered as different test bolus doses with an insulin pump to patients with T1DM during a standardized dinner meal	ΔAUC
To evaluate the intrasubject and intersubject insulin lispro PK variability of LY900014 compared with Humalog after 3 days of CSII	CV of AUC
To determine catheter occlusion rates with LY900014 and Humalog after 3 days of CSII	Microscopic assessment of infusion tubing after 3 days of use or in case of suspected catheter occlusion
To perform an exploratory comparison of glucose fluctuations with time in patients with euglycemia, hypoglycemia, and hyperglycemia receiving LY900014 and Humalog	CGM profiles during inpatient periods: time in euglycemia, hypoglycemia, and hyperglycemia

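### Read literally, the VAS pain table counts a patient in every category where any score falls, which inflates the low-pain rows and narrows the contrast between products

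*SAP*

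**What the plan says.** Pain at the infusion site is a named endpoint of the exploratory safety objective: Protocol Table ITSC.4.1 lists "infusion-site reactions/pain".

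SAP 9.5.9 plans two outputs. The first is general: "Data will be listed and summarized by treatment and bolus administration mode". The second is a category table with bands "0 mm, 1-10 mm, 11-20 mm, 21-30 mm, 31-40 mm, etc. up to the maximum category", laid out by treatment and timepoint, "and also the categories ≤ 10 mm, ≤ 20 mm and ≤ 45 mm". The count is defined in one sentence: "The table will show number and percent of patients with observations in each category". There is no rule for a patient with more than one score in a cell, and no denominator. All three cumulative rows face low pain, and no row is given for scores above 45 mm.

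The Protocol's Schedule of Activities (Section 2) has a score at minute 0 and then at "20, 40, 60, 120, 180, 240, 300" minutes after the breakfast bolus, on each of Days 1, 2 and 3. SAP Section 6 gives the safety outputs two treatment names, Humalog and LY900014, with bolus administration method as a separate factor.

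**The concern.** The table counts patients, but patients contribute repeated scores to its cells. Under the plain sense of the counting sentence, a patient belongs to every category in which he or she has a score. Suppose a patient has one score of 10 mm or less and five above 45 mm for a product at a given minute. That patient appears in a low band, in one or more high bands, and in all three cumulative rows.

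Two things follow. The exclusive bands no longer partition the patients, so their percentages can total more than 100%. The cumulative rows also become easy to enter, because one low score is enough. These are the rows a reader would use to say that a product is well tolerated, and the distortion runs in the favourable direction for both products.

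The SAP does set counting rules for other safety tables. SAP 9.5.1 takes the most severe grade of an adverse event for the summaries, and SAP 9.5.7 counts a hypoglycemic event once in its combined categories. The pain table has no equivalent.

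**Working it through.** The documents give no VAS rate, so there is no planned figure to reproduce.

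**Scores per cell.** In Protocol Table ITSC.5.1 every sequence gives each product in 2 of the 4 periods, and each period has 3 breakfast tests. Per patient, product and nominal minute this gives:

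- pooled over days and modes: 2 × 3 = 6 scores
- for one day, pooled over modes: 2 scores
- for one mode, pooled over days: standard dual-wave (SD) 2, rapid single-wave (RS) 1, standard single-wave (SS) 3 (total 6)
- for one mode and one day: 1 score

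The strata as written are products and timepoints ("up to the maximum category by treatment and timepoint"), so k is 6 or 2, depending on whether a timepoint includes the day.

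**Formula.** Let p be the chance that one score exceeds 45 mm and ρ the correlation between scores of the same patient. Neither is in the documents; both are assumed. A patient is missing from the ≤45 mm row only if all k scores exceed 45 mm:

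- independent scores: row = 1 − p^k
- correlated scores (beta-binomial): row = 1 − Π (a + i)/(s + i) for i = 0 to k − 1, with s = (1 − ρ)/ρ and a = p·s
- for k = 2 this reduces to row = 1 − [p² + ρp(1 − p)]

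**Worked case, k = 2, ρ = 0.5.**

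- p = 0.10: 1 − (0.01 + 0.5 × 0.09) = 94.5%
- p = 0.30: 1 − (0.09 + 0.5 × 0.21) = 80.5%

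**The ≤45 mm row for two products with p = 0.10 and p = 0.30.**

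| Scores per cell | ρ | p = 0.10 | p = 0.30 | Gap (points) |
|---|---|---|---|---|
| 1 | any | 90.0% | 70.0% | 20.0 |
| 2 | 0 | 99.0% | 91.0% | 8.0 |
| 2 | 0.5 | 94.5% | 80.5% | 14.0 |
| 6 | 0 | 100.0% | 99.9% | 0.1 |
| 6 | 0.3 | 99.4% | 96.2% | 3.2 |
| 6 | 0.5 | 97.9% | 90.6% | 7.3 |
| 6 | 0.7 | 95.4% | 83.3% | 12.1 |

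With ρ = 1 all of a patient's scores fall on the same side of 45 mm. Every row then equals 1 − p and the distortion is gone.

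**Upper end.** With independent scores and p = 0.20, the row is 1 − 0.2⁶ = 99.99% (k = 6) or 1 − 0.2² = 96% (k = 2). The share of patients with every score at or below 45 mm is only 0.8⁶ = 26% or 0.8² = 64%.

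**Worst-score count.** With k = 6 and ρ = 0.3, the share of patients with any score above 45 mm is 29.4% for p = 0.10 and 67.6% for p = 0.30, so the products are clearly apart. This count depends on k. For p = 0.10 and ρ = 0.3 it is 10.0%, 16.3% and 20.8% for k = 1, 2 and 3, which are the numbers of scores in the RS, SD and SS modes. Worst scores from different modes are therefore not comparable.

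**The case against.** The strongest reply is that the multiple counting is inferred. The sentence is ordinary wording for a table with one score per patient per cell, and the layout is left to the table shells (SAP Section 3), which are not among the documents. The schedule lists the scores by day, the preceding sentence of SAP 9.5.9 names bolus mode, and SAP 9.5.8 stratifies the neighbouring site assessment by treatment, mode and day. If the shells carry both mode and day into this table, there is one score per cell and no distortion.

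That stands as a possibility. But the category sentence names its own strata, and they include neither mode nor, expressly, day. One score per cell needs both. Each reading of the strata as written leaves at least 2.

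The second reply is that pain is visible elsewhere. The bands run to the maximum, so high scores have their own rows, and one high score places a patient there. Scores are also listed and summarized by treatment and mode. This also stands, with a limit: the band after 31–40 mm straddles 45 mm, and because a patient can sit in several bands, they cannot be added up to give the share ever above 45 mm.

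A reader might infer that the ≤45 mm row will read near 100% for both products whenever painful boluses are common, so that the table cannot tell a painful product from a painless one. The documents do not support that. Near-saturation needs about 6 pooled scores and low to moderate within-patient correlation. With 2 independent scores and half of all scores above 45 mm, the row is 1 − 0.5² = 75%.

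**Conclusion.** The point holds as a minor correction. Followed as written, the rule counts patients in more than one exclusive band and lets them into the ≤10, ≤20 and ≤45 mm rows on a single low score. Unless a patient's scores are perfectly correlated, this raises the low-pain rows. In the illustrated comparison, a 20-point gap between products shrinks to about 3 points (6 scores, ρ = 0.3) or 14 points (2 scores, ρ = 0.5).

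These sizes rest on assumed rates and correlations, and on the shells adding no strata or counting rule. The table as a whole does not hide frequent severe pain. It is one descriptive table under an exploratory objective, with no test or decision rule attached, and the primary inference on early 50% T_max is untouched.

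**What to change.** In SAP 9.5.9 and the table shell:

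1. Lay out the category table by product, bolus mode, day and minute, so that each patient contributes one score per cell. State the denominator as the patients with a score in that cell.
2. In any table pooled over days or modes, classify each patient once, by the worst score. Compare products within the same mode, because the modes supply unequal numbers of scores (SD 2, RS 1, SS 3).
3. Add a >45 mm row.

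The cost is a longer table or a small shell change, with a few sentences of SAP text and no new data. The rule should be fixed before the scores are examined, since SAP Sections 10 and 13 leave the sponsor and contract analysis teams unblinded during the trial.

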9.5.10 Exploratory Continuous Glucose Monitoring Analyses

The CGM outcome variables will be derived based on the raw data collected from the individualized standardized lunch meals on Days 1, 2, and 3 and from the individualized standardized dinner meals on Days 1 and 2.

The following incremental glucose AUCs will be calculated:

- AUC(0-1 h)
- AUC(0-2 h)
- AUC(0-5 h)

- AUC(2.5-5 h)

The incremental glucose AUCs will be calculated using the linear trapezoidal method (with negative areas included in the calculation of the trapezoidal areas). For the calculation of the incremental glucose AUC parameters, baseline is defined as the average of all CGM values recorded in the 19 minutes prior to each meal.

For the CGM data, time in range parameters will be derived from the raw data collected through the 3 days of CGM device use by patient, treatment, bolus dose administration method and meal. The following ranges will be calculated:

- Normal range (>70 mg/dL and ≤ 180 mg/dL) for each day, normalized to 5 hours (duration and % of 5 hours)
- Strict normal range (>70 mg/dL and ≤ 140 mg/dL) for each day, normalized to 5 hours (duration and % of 5 hours)
- Hyperglycemia (>180 mg/dL) during the treatment period, normalized to 5 hours (duration and also as % of 5 hours)
- Hypoglycemia (≤ 70 mg/dL) during the treatment period, normalized to 5 hours (duration and % of 5 hours)
- Severe hypoglycemia (≤ 55 mg/dL) during the treatment period, normalized to 5 hours (duration and % of 5 hours)

For the calculation of the incremental glucose AUCs and range parameters, the following rules will be used to define a valid CGM session prior to parameter calculation:

- Minimum number of measures for each parameter must be greater than 70% of the total measures obtained. For example, for iAUC(0-2 h), there will be 24 measurements during this period so a patient must have at least 17 valid measurements to be able to calculate the parameter. Similarly, for the time in range parameters calculated over 5 hours, there will be 60 measurements so must be at least 42 valid measurements to be able to calculate these parameters
- The maximum allowable continuous missing interval will be 10 minutes for incremental glucose AUC(0-1 h), 20 minutes for incremental glucose AUC(0-2 h) and incremental glucose AUC(2.5-5 h), and 25 minutes for incremental glucose AUC(0-5 h), Low blood glucose index (LBGI), high blood glucose index (HBGI), combined blood glucose risk index (BGRI, sum of the LBGI and HBGI), and the time in range parameters

The incremental glucose AUCs and time in range parameters will also be analyzed statistically with separate analyses based on the parameters at lunch times on Days 1, 2 and 3 only, and based on the parameters at Dinner times on Days 1 and 2 only. The model will include treatment (combination of treatment and bolus administration mode), period and day within period and treatment- by-day within period as fixed effects, and patient as a random effect. The model will be used to estimate least squares means, differences of least squares means of insulin lispro within LY900014 to Humalog by bolus administration mode, and the corresponding 90% CIs of the ratios.

In addition to the above parameters, within-day and between-day CGM variability parameters will be calculated. The within-day parameters (derived by day and meal) will include the standard deviation, CV% and Mean amplitude of glycemic excursions (MAGE). The between-day parameters will be based on the lunch data on Day 1-3 and dinner data on Days 1-2 separately, and will include the standard deviation, CV% and mean of daily differences (MODD).

The LBGI, HBGI and BGRI will also be derived. The LBGI has been developed to quantitate both frequency and severity of hypoglycemia. The LBGI has been validated as a predictor of severe hypoglycemia, which is a serious adverse event and could result in coma or death if unrecognized and untreated. The HBGI quantifies both frequency and severity of hyperglycemia and has been related to HbA1c and risk for hyperglycemia (Kovatchev et al. 2005). Additionally, both the LBGI and HBGI have a high sensitivity to changes in glycemic profiles and control (Kovatchev et al. 2005). LBGI is a non-negative number that increases as the number of low readings increases. HBGI is a non-negative number that increases as the number of high readings increases.

The LBGI, HBGI, and BGRI will be derived in the following steps:

Step 1: For each blood glucose (BG [mg/dL]) at the i^{th} time point, compute the following:

$$f(\text{BG}_i) = 1.509 \times [(\ln(\text{BG}_i))^{1.084} - 5.381]$$

Transform the BG data using a nonlinear transformation that maps the BG range of 20 to 600 mg/dL to a symmetric interval of $(-\sqrt{10}, \sqrt{10})$

The center of the BG scale is 112.5 mg/dL and is mapped to 0

Step 2: Compute BG risk for each reading

$$\text{rl}(\text{BG}_i) = 10 \times f(\text{BG}_i)^2 \text{ if } f(\text{BG}) < 0; \text{ otherwise } \text{rl}(\text{BG}_i) = 0$$

$$\text{rh}(\text{BG}_i) = 10 \times f(\text{BG}_i)^2 \text{ if } f(\text{BG}) > 0; \text{ otherwise } \text{rh}(\text{BG}_i) = 0$$

Assign the risk of each BG value by applying the above quadratic risk function

Range from 0 (achieved when BG = 112.5, the center) to 100

Left side of the parabola is risk of hypoglycemia, where the right side is risk of hyperglycemia

Step 3: Compute LBGI and HBGI

$$\text{LBGI} = \frac{1}{n} \sum_{i=1}^n \text{rl}(\text{BG}_i), \text{ where } n \text{ is the number of measurements}$$

$$\text{HBGI} = \frac{1}{n} \sum_{i=1}^n \text{rh}(\text{BG}_i), \text{ where } n \text{ is the number of measurements}$$

Step 4: Compute BGRI

$$\text{BGRI}_m = \text{LBGI} + \text{HBGI}$$

The calculated parameters will be summarized and listed by treatment, bolus dose administration mode, day and meal. In addition, the average across the three days for lunch and two days of dinner will be calculated separately.

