7. SAMPLE SIZE JUSTIFICATION

An initial 24 patients may be randomized in order that approximately 20 patients complete the study. Twenty completing patients will provide approximately 80% power to demonstrate a 25% decrease in the time to early half-maximal concentration (early 50% T_{max}) between LY900014 and Humalog. Testing will be done at an α -level of 0.1 with a 2-sided confidence interval (CI). The variability was estimated by analyzing internal Lilly data (CCI [REDACTED]) for LY900014 and Humalog administered on CSII therapy, resulting in approximately 35.9% coefficient of variation of within-patient variability for early 50% T_{max}. Patients who are randomized but drop out before completing assigned treatment may be replaced to ensure that approximately 20 patients complete the study (refer to Section 5.1).

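### The CGM lunch and dinner models have no patient-by-period term, so the 90% CI for a day-averaged LY900014-Humalog difference is too narrow if same-period meals are positively correlated

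*SAP*

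**What the plan says.** SAP 9.5.10 plans "separate analyses based on the parameters at lunch times on Days 1, 2 and 3 only" and a second set "based on the parameters at Dinner times on Days 1 and 2 only". The fixed effects are the treatment-mode combination, period, day within period and treatment-by-day within period. The random part is patient alone: "treatment- by-day within period as fixed effects, and patient as a random effect". The section gives no code, REPEATED structure or degrees-of-freedom method.

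The requested output is "differences of least squares means of insulin lispro within LY900014 to Humalog by bolus administration mode", with "the corresponding 90% CIs of the ratios". SAP 9.3.2 asks for the breakfast PK ratios by day as well as by mode; the CGM sentence names mode only.

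On design, SAP section 5 and Table 1 assign one formulation per period and repeat the same lunch mode and the same dinner mode on every day of that period. The catheter stays at one site for the three days (SAP section 5). The CGM device is worn from before the Day 1 breakfast until after the Day 3 lunch (protocol 9.6.3). Protocol 10.3.4 leaves the CGM analysis details to the SAP.

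**The concern.** Because formulation and mode do not change within a period, LY900014 versus Humalog in a given mode always compares one period of a patient with another. The two or three meals in a period are repeated measures on that unit. The fixed period and day terms describe shifts common to all patients; they cannot absorb one patient's own deviation in one period, such as an effect of that catheter site or that sensor. With patient as the only random effect, such a deviation is counted as independent meal-level noise and averaged down as if each meal supplied a fresh draw.

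At stake is the stated precision of the lunch and dinner comparisons, which are named exploratory objectives. SAP 9.1 also allows significance to be claimed at p<0.1 unless otherwise specified. An interval that is too short would claim more certainty about those differences than the data hold.

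**Working it through.** **The plan's own figure.** No power or CI width is stated for CGM. The one design figure concerns breakfast PK: "Twenty completing patients will provide approximately 80% power to demonstrate a 25% decrease in the time to early half-maximal concentration", from "approximately 35.9% coefficient of variation of within-patient variability".
- Log-scale SD = sqrt(ln(1 + 0.359²)) = 0.348.
- SE = 0.348 × sqrt(2/20) = 0.110; |ln 0.75| = 0.288; noncentrality 0.288/0.110 = 2.61.
- Noncentral t, 19 df, two-sided 0.10: power 80.9%.

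The figure reproduces, and the present point does not touch it.

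**Inputs for the CGM check.** From the documents: 20 completers, four periods, the four sequences of Table 1, k = 3 lunches or k = 2 dinners per period, 90% intervals. Assumed: rho, the share of within-patient variance that belongs to patient-by-period. The main range is 0.1 to 0.3.

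**Formula.** Set the within-patient variance to 1.
- True variance of a period mean: (1 + (k−1)rho)/k.
- The patient-only model uses s²/k. In this balanced design E(s²) = 1 − rho + rho × k × 54/df. Here 54 is the residual df of the period means, and df is the model's own error df: 200 for lunch, 127 for dinner.
- Variance ratio R = (1 + (k−1)rho)/E(s²). Approximate coverage = 2Φ(1.645/√R) − 1.

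**Lunch, k = 3**, E(s²) = 1 − 0.19 rho:
- rho 0.1: R = 1.2/0.981 = 1.223; coverage 86.3%.
- rho 0.2: R = 1.4/0.962 = 1.455; coverage 82.7%.
- rho 0.3: R = 1.6/0.943 = 1.697; coverage 79.3%, so about 21% error against a nominal 10%.

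**Dinner, k = 2**, E(s²) = 1 − 0.15 rho:
- rho 0.1: R = 1.1/0.985 = 1.117; coverage 88.1%.
- rho 0.3: R = 1.3/0.955 = 1.361; coverage 84.2%.

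**Simulation** of the Table 1 design, 4,000 trials per setting. Ranges cover two versions of the fixed effects, with the day terms crossed with period or fully nested in it.

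| Meal | rho | Coverage, patient only | Coverage with patient-by-period | Width factor |
|---|---|---|---|---|
| Lunch | 0 | 0.90 | 0.90 | 1.01 |
| Lunch | 0.1 | 0.86-0.87 | 0.90 | 1.11 |
| Lunch | 0.3 | 0.78-0.79 | 0.89-0.90 | 1.32 |
| Dinner | 0 | 0.90 | 0.90 | 1.01 |
| Dinner | 0.1 | 0.88-0.89 | 0.90 | 1.06 |
| Dinner | 0.3 | 0.84 | 0.90 | 1.17 |

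For larger rho, 0.5 to 0.7, patient-only coverage falls to about 0.73 to 0.67 (lunch) and 0.80 to 0.77 (dinner). A single-day contrast from the same patient-only model covers 0.88 to 0.90 across the whole range from 0 to 0.7. Error df fall from 176-200 (lunch) or 112-127 (dinner) to 48-54 once the period is treated as the unit.

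**The case against.** The strongest reply is that the covariance structure is unstated rather than wrong. SAP 9.3.2 also describes patient as a random effect, yet its code groups that effect by treatment-mode combination. Each combination fills exactly one period per patient, so that code would model within-period correlation. This does not rescue the CGM section. SAP 9.4.2 explicitly carries the PK model over to the glucodynamic analysis, whereas 9.5.10 writes its own model and does not refer to that code. Borrowing it would also drop the correlation between a patient's periods. Simulated coverage was then 0.98 to 1.00, assuming between-patient variance equal to total within-patient variance, so the intervals would be too wide.

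Other parts of the reply stand:
- The documents give no value for the correlation, and at zero there is no error. A reader might infer that the intervals are certainly too narrow; the documents support only the conditional statement.
- Incremental AUC subtracts the mean CGM value over the 19 minutes before each meal, so a constant sensor offset cancels. A gain error would not, and time in range has no such correction.
- Periods may follow on consecutive days, so slow drift in insulin sensitivity could be shared by adjacent periods and need not be specific to one.
- The two normal ranges are defined for each day, but the hyperglycemia and two hypoglycemia ranges are defined over the treatment period. If those three yield one value per period and meal, they have no repeats and the problem does not arise.
- The model contains a treatment-by-day term and CGM parameters are summarized by day. Averaging over days is read from the phrase asking for differences by mode; it is not stated.
- The analysis is exploratory. Nine parameters, two meals and two modes make 36 contrasts with no multiplicity control, so strict control of error at 10% was never promised.

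**Conclusion.** The point holds in conditional form. As SAP 9.5.10 is written, the nominal 90% CI for the day-averaged LY900014-Humalog difference by mode under-covers whenever meals in the same period are positively correlated beyond the patient effect. The shared catheter site and CGM wear make that plausible but do not fix its size. For an assumed correlation of 0.1 to 0.3, coverage is about 87% to 79% for lunch and 88% to 84% for dinner. The calculation assumes 20 completers with complete data and equal variances across treatments.

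The scope is limited to CGM parameters with one value per meal-day. A reader might infer that the primary result is at risk. It is not: the only decision rule concerns breakfast early 50% Tmax, which has its own model. Nor does the point extend to single-day CGM contrasts, where the loss is at most about two percentage points. It is still worth correcting, because the stated random structure ignores the unit on which treatment varies and the remedy is one model term.

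**What to change.** In SAP 9.5.10, for every lunch and dinner CGM model with more than one value per period:
- add a patient-by-period random intercept to the patient effect (for example `random patient patient*period`), or specify an equivalent compound-symmetric or unstructured day covariance within patient-period;
- state Kenward-Roger degrees of freedom, as SAP 9.3.2 already does for PK;
- state whether the LY900014-Humalog contrasts are by day or averaged over days;
- state whether the hyperglycemia and hypoglycemia ranges give one value per day or one per period.

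The same sentence asks for differences of least squares means but CIs of ratios; that should be reconciled in the same edit.

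The cost is one extra term. If the correlation is zero, intervals widen by about 1%. At 0.1 to 0.3 they widen by about 11-32% for lunch and 6-17% for dinner, which is uncertainty that the present model hides. No change to sample size, data collection or the primary analysis is needed.
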